The sample consisted of 36 women and 13 men, divided into two age groups: young people between 18 and 30 years old ($22,438 \pm 3,898$) and adults between 31 and 64 years old ($50,212 \pm 9,633$). In terms of origin, 23 were residents of Plasencia (Spain) and 26 in Castelo Branco (Portugal). The descriptive characteristics of the sample are detailed in Table 1.

Table 1. Descriptive characteristics of the sample.

VARIABLES	Total n=49	Origin	Young Men (mean±SD)	Adult Men (mean±SD)	Young Women (mean±SD)	Adult women (mean±SD)
AGE (years)	41,143± 15,485	Spain Portugal	20±2,828 26±NP	46,333±13.317 46,857±10,495	24,111±3,723 19±2	49±9,367 53.50±8.609
	70,545± 12,705	Spain Portugal	80±14,142 69±NP	87,333±17,926 80,714±11,572	68,667±13,684 66,750±8,995	64,411±7,193 66.857±11.016
HEIGHT (m)	1,664±0 ,085	Spain Portugal	1.82±0.113 1.7±NP	1.733±0.025 1.757±0.060	1,652±0.074 1.657±0.049	1.618±0.068 1,616±0.057
	25,404± 3,626	Spain Portugal	24,026±1,280 23,875±np	29,170±6,725 26,148±3,488	25,069±4,334 24,372±3,837	24,611±2,350 25,552±3,548

n: sample size; SD, standard deviation; NP: Not applicable; kg: kilogram; M: Metro; BMI, body mass index; m^2 : Square meter.

Randomization, masking, and experimental design

Participants were randomly assigned to distinct groups using free software Epidat 4.0 (2011, Galicia, Spain). The blinding was double-blind, so that neither the investigators nor the participants knew the group assigned to the participant until the completion of the study and statistical analysis.

The total number of participants was divided into three groups: a control group (T0) (n=12), in which no participants had a skin infection, and two different treatment groups (T1 and T2) (n=37), with diverse levels of EC. The rest of the participants were included in these two treatment groups, including both infected (n=32) and healthy (n=5) participants. Thus, group T1 (n=25) had 23 participants with infection and 2 healthy participants, and group T2 (n=12) had 9 participants with infection and 3 healthy participants.

The clinical evaluation of the participants was carried out before the start of treatment and, subsequently, on days 15, 30, 45 and 60 of treatment, except for cultures, both mycological and bacterial, which were performed at baseline, at 30 days and at 60 days of treatment. All reviews, sampling, and data collected were performed by the same observer.

Choice of EO, base cream, and preparation of treatments

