Scans and measurements were performed in a temperature-controlled room (20-24°C) and participants aired their bare feet for 10 minutes before starting the procedures, to normalize the temperature. In the first session they were weighed and measured (SECA 701, Vogel & Halke Hamburg, Germany), calculating the BMI(2). After normalizing the temperature, the physical examination was carried out, samples were taken, and data were obtained.

The Corneometer CM 825® (Electronic Courage-Khazaka, Cologne, Germany) with a measuring surface of 49 mm, a frequency of 0.9–1.2 MHz and an accuracy of $\pm 3\%$, was used to assess the superficial hydration of the skin (3). Five reference points were measured, both at the dorsal level and at the plantar level (Figure 2), obtaining three measurements from each point to later calculate the average hydration of each location analyzed.

[figure not shown]

Figure 2. Location of the 5 reference points on the feet for assessment of superficial hydration. (A) Dorsum of the foot: (1) dorso-distal point, above the central metatarsal heads. (B) Sole of the foot: (2) interdigital-plantar point, between 3rd and 4th digital space, (3) central point of the internal arch, (4) central point of the external arch, and (5) central point of the calcaneus.

Regarding the diagnosis of possible infections present in the feet, the following tests were performed:

- Wood's Light Examination

The feet of the participants were examined with a Wood L1004® lamp (Weelco, Barcelona, Spain) at maximum power (41) and at a distance of 10-15 cm from the surface to be examined. Long-wave ultraviolet radiation allows visual observation of the fluorescence emitted by *Pseudomonas aeruginosa*, *Microsporum audouinii*, *Microsporum canis*, *C. minutissimum*, *T. schoenleinii*,(4) among

others, whose color varies depending on the pathogen. The areas that fluoresced were recorded along with the color of the fluorescence in each review conducted from the beginning of the study to the day of its completion.

- Potassium hydroxide (KOH) test and mycological culture

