Statistical analysis was performed using the statistical analysis program IBM-SPSS Statistics for Windows version 25 (IBM Corp. Armonk, NY, USA). Some figures have been obtained using the Python programming language, using the Seaborn library (Waskom, M. L., (2021). Seaborn: statistical data visualization. *Journal of Open-Source Software*, 6(60), 3021, <https://doi.org/10.21105/joss.03021>).

Normality was assessed using the Shapiro-Wilk test. To evaluate the influence of different variables on infection remission, a Cox regression model was used, and survival curves of significant factors were plotted. To compare the efficacy of different EC concentrations, survival curves were compared using the Log-rank test. The Mann-Whitney U test was used to assess hydration averages according to sex. To check if there were improvements in hydration due to the use of the cream with different concentrations of EC (T1 and T2) compared to the control group (T0), hydration levels were compared using Kruskal-Wallis tests, using the Mann-Whitney U test with correction of p-values by the Bonferroni method for multiple comparisons.

In all statistical tests, significance was considered when p-value<0.05 and high significance when p-value<0.01.

2. Results

Analysis of the Elemental Composition of Commercial S. S.

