	Man	21.644±15.004		26.911±16.238		24.792±13.615		24.906±15.583		23.601±11.566	
External Arc R	Woman	19.661±10.161	0.180	23.534±14.690	0.679	24.834±12.267	0.147	22.125±6.492	0.626	22.006±12.310	0.087
	Man	15.241±8.282		22.537±15.051		21.120±17.939		21.646±13.670		15.783±6.355	
Heel R	Woman	15.655±12.504	0.051*	22.007±17.183	0.087	24.039±16.469	0.010**	20.392±15.543	0.044*	16.369±9.456	0.019*
	Man	9.405±5.241		13.295±9.737		13.218±11.013		12.085±6.642		10.163±5.772	
Dorsal L	Woman	33.660±11.527	0.132	37.629±10.449	0.519	41.001±11.869	0.075	41.194±12.604	0.062	40.777±13.844	0.164
	Man	28.085±9.337		34.736±10.806		33.799±15.305		33.745±18.116		33.668±12.444	
Digital plant L	Woman	27.532±14.373	0.028*	33.285±15.653	0.548	32.845±18.542	0.180	31.167±16.393	0.103	30.706±15.793	0.048*
	Man	18.307±8.845		31.372±15.814		24.748±11.505		22.863±9.201		20.941±11.391	
Inner Arch L	Woman	25.227±18.044	0.509	25.921±17.105	0.497	30.068±21.122	0.217	24.222±14.493	0.319	27.622±17.542	0.111
	Man	21.662±16.214		23.418±15.999		21.847±11.934		19.917±12.615		20.309±13.074	
External Arc L	Woman	18.237±11.858	0.022*	20.679±12.047	0.679	22.122±10.429	0.045*	19.848±13.604	0.448	19.494±9.876	0.012*
	Man	11.614±4.385		20.008±12.647		16.649±11.251		16.387±8.587		12.575±5.412	
Heel L	Woman	16.168±11.812	0.012*	18.131±13.019	0.167	24.513±20.395	0.062	16.580±14.922	0.038*	14.351±9.984	0.010**
	Man	8.765±4.557		13.095±9.544		12.488±7.218		9.045±5.445		7.762±4.338	

R: right; L: Left; Sd: standard deviation; *: significant; **: Highly significant.

On the other hand, in relation to skin hydration, it was obtained that the three groups had similar hydrations at the beginning of the study, although it is true that it was observed that the hydration of the T2 group decreased throughout the treatment, being lower at the end of the treatment in all the measured points except for the left dorsal point, where a marked increase in hydration was observed after a month and a half of treatment (Figure 7).

[figure not shown]

Figure 7. Evolution of hydration of the different points of the foot over the study time according to the test group.

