Although descriptively variations in skin hydration are observed depending on the treatment applied, only the area of the "Outer Arch" of the right p-ie showed significant differences between groups, both at one and a half months of treatment ($p\text{-value}=0.028$) where the T1 group presented a lower hydration, and at its completion ($p\text{-value}=0.002$), with the T2 group having the lowest hydration (Table 1-1). After the pairwise comparison, statistically significant differences were obtained between the T0 and T1 groups at one and a half months ($p\text{-value}=0.016$), observing that the control group had greater hydration, and between the T0 and T1 groups ($p\text{-value}=0.021$) and the T0 and T2 groups ($p\text{-value}=0.003$) at the end of treatment where, as in the month and a half, the control group had greater hydration (Table 1-2).

Table 11. Results of the Kruskal-Wallis tests for the analysis of hydration as a function of time and treatment applied.

Landmarks per foot	G	Clinical Evaluation							
		Initial		15 days		30 days		45 days	
		Media±Sd	p-value	Media±Sd	p-value	Media±Sd	p-value	Media±Sd	p-value
Dorsal R	G. T0	35,506±9,364		46,356±17,565		47,787±18,500		41,144±12,744	47,612±19,149
	G. T1	32,481±9,077	0.600	39,537±14,093	0.405	42,690±16,888	0.669	40,626±13,840	0.775
	G. T2	32,095±12,123		41,366±13,255		43,522±11,821		43,332±13,482	41,433±17,052
Digital Plant R	G. T0	29,630±8,215		38,992±17,156		44,454±18,161		38,044±17,682	36,998±18,832
	G. T1	26,538±13,104	0.592	37,230±17,615	0.943	32,939±14,430	0.059	32,126±14,095	0.474
	G. T2	28,846±12,171		36,666±10,250		29,616±12,832		36,225±11,886	27,466±13,514
Inner Arc R	G. T0	31,117±15,186		31,721±18,640		35,890±23,178		32,205±18,994	37,761±17,694
	G. T1	28,705±22,666	0.135	33,491±24,892	0.687	29,179±18,094	0.457	28,441±20,519	0.633
	G. T2	17,731±9,006		25,278±12,703		25,831±17,795		24,487±9,525	21,633±11,244
External Arc R	G. T0	20,622±9,449		24,434±14,194		27,500±13,395		29,243±12,342	27,668±9,032
	G. T1	19,081±10,643	0.336	24,125±15,356	0.701	24,190±14,910	0.317	18,564±12,384	0.028*
	G. T2	15,119±8,104		20,323±14,354		19,487±11,907		20,989±11,010	13,874±7,691
Heel R	G. T0	14,873±9,495		19,435±13,382		28,527±20,929		21,406±16,765	17,062±7,272
	G. T1	14,966±14,056	0.654	21,629±19,017	0.778	19,897±13,953	0.212	17,934±15,610	0.898
	G. T2	11,102±5,294		15,928±10,798		16,457±12,132		15,501±6,685	11,152±6,825

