Dorsal L	G. T0	33,012±8,530		38,395±7,423		42,575±9,287		33,613±15,368	38,689±15,840
	G. T1	32,565±12,148	0.678	35,652±10,539	0.586	37,758±15,290	0.353	38,750±11,631	0.350
	G. T2	30,550±12,090		37,848±13,328		38,380±11,603		45,797±17,274	40,447±16,602
Digital plant L	G. T0	26,513±10,342		31,862±12,709		36,755±21,018		32,947±14,918	29,832±17,134
	G. T1	26,507±16,982	0.418	34,129±18,575	0.874	29,028±16,213	0.378	28,648±16,907	0.360
	G. T2	20,692±7,252		30,878±11,501		28,115±15,045		25,639±11,464	23,191±12,778
Inner Arch L	G. T0	30,085±18,613		24,526±14,755		30,087±18,498		25,663±14,024	33,847±17,840
	G. T1	24,558±18,120	0.107	27,108±18,847	0.962	27,772±21,308	0.663	23,644±16,181	0.672
	G. T2	17,902±13,773		22,131±14,279		25,928±17,070		19,322±8,165	19,328±6,947
External Arc L	G. T0	17,284±8,118		22,680±13,574		27,284±14,439		23,026±11,456	20,305±9,256
	G. T1	24,558±18,120	0.467	20,511±11,508	0.767	18,256±7,641	0.170	18,480±14,599	0.213
	G. T2	17,902±13,773		18,300±12,370		19,084±10,512		15,772±7,333	13,408±5,542
Heel L	G. T0	14,813±11,394		16,564±11,596		24,016±21,500		17,476±12,617	11,199±5,958
	G. T1	15,070±12,280	0.743	17,430±14,041	0.963	20,608±15,971	0.467	14,765±16,442	0.486
	G. T2	11,789±6,844		15,705±9,684		20,119±21,826		11,302±4,496	11,412±6,345

R: right; L: Left; G: group; G. T0: control group; G T1: T1 treatment group; G T2: T2 treatment group; Sd: standard deviation; *: significant; **: Highly significant.

Table 12. Mann-Whitney U test with Bonferroni p-value correction for outer arch hydration data at one and a half months and completion of treatment.

			p-value	Adjusted p-value
External arch after a month and a half of treatment	No treatment (T0)	Treatment 1% (T1)	0.008**	0.023*
	No treatment (T0)	Treatment 0.5% (T2)	0.092	0.276
	Treatment 1% (T1)	Treatment 0.5% (T2)	0.476	1.000
External arch at the end of treatment	No treatment (T0)	Treatment 1% (T1)	0.008**	0.024*
	No treatment (T0)	Treatment 0.5% (T2)	0.001*	0.002**
	Treatment 1% (T1)	Treatment 0.5% (T2)	0.211	0.632

*: meaningful; **: Highly significant.

Bibliography

1. Spanish Agency for Medicines and Health Products (AEMPS). Compendium of European standards and guidelines relating to cosmetic products for the application of the regulation 1223/2009 [Internet]. 2019. Available from: <https://www.aemps.gob.es>
2. Quetelet ALJ. *Fisica sociale ossia svolgimento delle facolta dell'uomo*. 1869.

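### Hydration is compared between arms on raw levels in 40 site-by-visit tests at 0.05 each, with Bonferroni over the three arm pairs only and baseline not modelled; on the published p-values day 45 fails over the 40 and day 60 depends on method and family.

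*Combined protocol and SAP*

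**What the plan says.** The section on variables and statistical analysis sets out to see whether the enriched creams improve hydration relative to control, and states that "hydration levels were compared using Kruskal-Wallis tests, using the Mann-Whitney U test with correction of p-values by the Bonferroni method for multiple comparisons". The threshold is general: "In all statistical tests, significance was considered when p-value<0.05".

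The number of comparisons follows from the design. Under exploration and sampling, "Five reference points were measured, both at the dorsal level and at the plantar level"; Table 11 lists each point separately for the right and left foot. The post-baseline evaluations are "on days 15, 30, 45 and 60 of treatment". No site or visit is named as primary.

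Baseline hydration appears only as a balance statement in the Results: "the three groups had similar hydrations at the beginning of the study". The Results then report that only the right outer arch "showed significant differences between groups, both at one and a half months of treatment" (p=0.028) and at completion (p=0.002), and that at the end, "as in the month and a half, the control group had greater hydration". Table 12 is headed "Mann-Whitney U test with Bonferroni p-value correction for outer arch hydration data at one and a half months and completion of treatment".

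**The concern.** A correction is named, so a reader may think multiplicity is covered. It covers the three arm pairs inside a single site and visit, and nothing covers the 40 site-by-visit tests from which the one positive site emerged.

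The stated question is improvement, but the quantity tested is the level at each visit. A level mixes any difference present before treatment with change on treatment, and the baseline values needed to separate the two were collected.

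At stake is the only between-arm hydration difference reported: that control skin was better hydrated than skin treated with the enriched creams. The published right outer arch figures also conflict with one another, so they need a source check before any re-analysis.

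**Working it through.** **1. Family size.** 5 points x 2 feet x 4 visits = 40 three-arm tests, or 40 x 3 = 120 arm-pair comparisons. If all 40 nulls held and the tests were independent, 40 x 0.05 = 2 significant results would be expected, and P(at least one) = 1 - 0.95^40 = 0.87. Two are reported. At an assumed common correlation of 0.5, simulation puts P(at least one) at about 0.58.

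**2. Reproducing Table 12.** Adjusted p = min(1, 3 x raw p):
- Day 45: 3 x 0.008 = 0.024 (printed 0.023); 3 x 0.092 = 0.276 (0.276); 3 x 0.476 is capped at 1 (1.000).
- Day 60: 3 x 0.008 = 0.024 (0.024); 3 x 0.001 = 0.003 (0.002); 3 x 0.211 = 0.633 (0.632).

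All six agree within the rounding of the raw p-values, so the factor is 3.

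**3. Published p-values over the 40 tests.** The day-60 value of 0.002 may lie anywhere from 0.0015 to 0.0025.

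| Method | Day 45 (0.028) | Day 60 (0.002) |
|---|---|---|
| Bonferroni, p x 40 | 1 | 0.08 (0.06-0.10) |
| Holm | 1 | 0.08 |
| False discovery rate | 0.18-0.56 | 0.08 |
| Simulated min-p, assumed common correlation 0 / 0.3 / 0.5 / 0.7 | 0.63 / 0.52 / 0.40 / 0.27 | 0.044 / 0.044 / 0.035 / 0.025 (0.058-0.019 with rounding) |
| Ten day-60 tests only, p x 10 | not applicable | 0.02 |

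The day-45 false-discovery range reflects nine day-60 p-values that are not legible in the extracted Table 11. They were set between 0.0501 and 0.5, because the text says only this site differed. By Bonferroni, day 60 passes in any family of up to 0.05/0.002 = 25 tests (20 to 33 with rounding).

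Multiplying Table 12's adjusted pairwise values by 40 gives 0.92 (day-45 T0-T1), 0.96 (day-60 T0-T1) and 0.08 (day-60 T0-T2).

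**4. Baseline share at the flagged site** (Table 11, right external arch).
- Day-60 T0-T2 gap: 27.668 - 13.874 = 13.79.
- Baseline T0-T2 gap: 20.622 - 15.119 = 5.50, which is 5.50/13.79 = 40% of the day-60 gap.
- Difference in change: 13.79 - 5.50 = 8.29.
- Two-arm ANCOVA gap: 13.79 - r x (8.39/8.80) x 5.50, with pooled SDs 8.39 (day 60) and 8.80 (baseline). This is 12.2 at an assumed within-arm baseline correlation r = 0.3 and 9.6 at r = 0.8.

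**5. Can the adjusted p-value be foreseen?** The documents do not give r. A normal-theory three-arm ANCOVA from Table 11's day-45 means and SDs gives p of about 0.056, 0.037, 0.010 and 0.002 at r = 0.3, 0.5, 0.7 and 0.8. At r = 0.82 it is about 0.001, below the Bonferroni limit of 0.05/40 = 0.00125. The day-60 T0-T2 two-arm ANCOVA gives p of about 0.0023 at r = 0.3 and 0.0003 at r = 0.8. Either visit could therefore become weaker or stronger.

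**6. Conflicts at the flagged site.** Right external arch, day 45:
- Table 10 total sum of squares: 35 x 6.492^2 + 12 x 13.670^2 + 2 (between sexes) = 3,720.
- Table 11 within-arm sum alone: 11 x 12.342^2 + 24 x 12.384^2 + 11 x 11.010^2 = 6,690. A part cannot exceed the total for the same 49 people.
- Overall means: (36 x 22.125 + 13 x 21.646)/49 = 22.00 from Table 10; (12 x 29.243 + 25 x 18.564 + 12 x 20.989)/49 = 21.77 from Table 11.

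The text before Table 11 gives pairwise p-values of 0.016, 0.021 and 0.003. For the same comparisons Table 12 has 0.008, 0.008 and 0.001 raw, and 0.023, 0.024 and 0.002 adjusted. The text matches neither column.

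**The case against.** The strongest reply is that the family of 40 is the reviewer's choice. A reader interested in end of treatment would count ten tests, and day 60 then passes at 0.02. That stands as a sensitivity result. It does not rescue the plan, because no visit was named as primary and the positive claim covers two visits.

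A second reply is that the result favours control, so no claim of benefit is overturned, and that T0 is not a like-for-like comparator anyway: 0 of 12 infected, against 23 of 25 in T1 and 9 of 12 in T2. Both parts are right, and they limit the consequence. They do not make an uncorrected statement about control hydration sound.

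Three stronger readings are tempting, and the documents do not support them.
- **That both differences would vanish on re-analysis.** The failure at day 45 is shown only for the published, unadjusted p-values. At a baseline correlation of about 0.8 or more, either visit could strengthen and their order could reverse.
- **That a three-arm ANCOVA shows day 60 failing clearly.** The T1 day-60 value is not in the extracted Table 11. Rebuilding it from Table 10 gives 19.96 (SD 12.01), but the same method at day 45 of this site gives a T1 mean of 19.00 against the printed 18.564, and a negative sum of squares (-155). Any day-60 three-arm figure built this way is illustrative at most.
- **That only the women's SD of 6.492 in Table 10 is wrong, leaving the arm comparison untouched.** It is the likelier fault, since Table 11 implies about 12.4. But the overall means disagree as well, so a fault in Table 11 is not excluded.

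**Conclusion.** The concern holds, in a limited form. Forty raw-level tests at 0.05 each, a correction over three pairs only, and an unmodelled baseline all follow directly from the text and tables.

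On the published p-values, the day-45 difference does not survive correction over the 40 tests. The day-60 difference is unsettled: it misses under Bonferroni or Holm, mostly passes under a correlation-aware method, and passes in a ten-test family. The min-p figures rest on an assumed common correlation of 0 to 0.7, and the ANCOVA figures on an assumed baseline correlation and normal theory.

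The 40% baseline share is arithmetic from Table 11 and shows that raw levels overstate the T0-T2 difference in change at this site. It does not show that the difference is absent. Confounding of T0 with infection status remains under any correction.

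**What to change.** **Re-analysis.** Analyse post-baseline hydration with same-site baseline as covariate, using rank ANCOVA if the data are not normal. Use the three-arm test as gatekeeper for the arm pairs and apply Holm over all 40 site-by-visit tests. Label the results exploratory and show the ten-test day-60 family as a sensitivity analysis. State that contrasts with T0 are confounded with infection status; with only 5 uninfected treated participants (2 in T1, 3 in T2), adjustment cannot resolve this precisely.

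**Source check first.** Verify the right external arch at day 45 in both Table 10 and Table 11, means as well as SDs. Reconcile the pairwise p-values in the text with Table 12.

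**Separate minor corrections.**
- The left external arch baselines for T1 and T2 in Table 11 repeat those of the left inner arch. The overall mean is 16.48 from Table 10 and 21.15 from Table 11.
- The right dorsal day-30 overall means differ: 44.36 from Table 10 and 44.14 from Table 11.
- The statement that T2 hydration fell during treatment needs its reference. At the nine sites with a usable baseline, T2 rose by day 15 at all nine and ended above baseline at six. Against T0 at day 60 it is lower at eight of ten.

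**Cost.** A re-run of existing data plus table and text corrections, with no new data. The reported significant differences may be lost or may change.
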